8.2. Analyses of Other Secondary Efficacy Endpoints

Other secondary endpoints to be assessed include:

- Change and percent change from baseline in IOP at each timepoint/post-baseline visit
- Change and percent change from baseline in mean diurnal IOP at each post-baseline visit
- Having a mean diurnal IOP reduction $\geq 20\%$, $\geq 25\%$, or $\geq 30\%$ from Baseline (Visit 2) at each post-baseline visit

- Having a mean diurnal IOP $\leq 18\text{mmHg}$ at each post-baseline visit

For continuous secondary endpoints (change and percent change from baseline in IOP/mean diurnal IOP) at Week 1 (Visit 3), Week 6 (Visit 4), and Month 3 (Visit 5), both an analysis using a MMRM will be performed and descriptive summaries will be generated. The MMRM will be analogous to the MMRM used in the analysis of the primary endpoint. For both the analysis using MMRM and descriptive summaries of the IOP or mean diurnal IOP (raw) scores, IOP values obtained after using rescue therapy will be censored (i.e., treated as missing).

For the following binary secondary endpoints, the responder rates will be analyzed using the Pearson's chi-square test for a 2×2 contingency table; differences between the DE-117 and Timolol arms will be reported along with corresponding p-values:

- Having a mean diurnal IOP reduction $\geq 20\%$, $\geq 25\%$, or $\geq 30\%$ from Baseline (Visit 2) at each post-baseline visit
- Having a mean diurnal IOP $\leq 18\text{mmHg}$ at each post-baseline visit

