##### **14.7.2.2. Other Secondary Efficacy Endpoints**

Other secondary endpoints to be assessed include:

- Change and percent change from baseline in IOP at each timepoint/post-baseline visit
- Change and percent change from baseline in mean diurnal IOP at each post-baseline visit
- Having a mean diurnal IOP reduction  $\geq 20\%$ ,  $\geq 25\%$ , or  $\geq 30\%$  from Baseline (Visit 2) at each post-baseline visit
- Having a mean diurnal IOP  $\leq 18$  mmHg at each post-baseline visit

The Continuous secondary endpoints will be analyzed using MMRM on observed cases. More details on the model specifications will be provided in the SAP.

The binary secondary endpoints will be analyzed using the Pearson's chi-square test for a  $2 \times 2$  contingency table. The Fisher's Exact test may be conducted as a sensitivity analysis.

Subgroup analyses may be performed for secondary endpoints using descriptive statistics.

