3.2. Randomization and Masking

A blocked randomization stratified by age (< 18 and ≥ 18 years old) will be employed to randomize eligible subjects in a 1:1 ratio to receive either DE-117 or Timolol. The randomization schedule will be generated and implemented by an independent CRO, Medidata Solutions, Inc. (New York City, NY).

This is a double-masked study. The subjects, Investigators, Examiners, and Santen personnel involved in the conduct of the study will be masked to the study treatment. An authorized unmasked study staff member who is not the Investigator or Examiner at the investigative site

will dispense and collect study medication(s) and will query about dosing compliance. In case of a medical emergency, when the unmasking of a subject's treatment assignment code becomes necessary for the welfare of that subject, the Clinical Investigator may reveal the treatment information by unmasking which treatment the subject has received through the study's interactive web response system (Medidata RTSM).

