3.3. Sample Size Planning

The sample size calculation was based on a two-sided Type I error rate of 5% and a non-inferiority margin of 1.5 mmHg. Assuming a treatment difference of 0 mmHg between the DE-117 arm and the Timolol arm, a standard deviation (SD) of 4.0 mmHg, and a correlation coefficient of 0.6 among repeated measures, approximately 400 adult subjects in total (200 subjects per treatment arm) will provide 90% power to demonstrate non-inferiority of DE-117 Ophthalmic Solution 0.002% to Timolol Maleate Ophthalmic Solution 0.5% in IOP-lowering effect.

The standard deviation of 4.0 mmHg was determined from previous DE-117 studies conducted in the United States: 33-002 and 33-003.

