6. GENERAL CONSIDERATIONS

All measures will be summarized by treatment (planned or actual received) descriptively. Continuous variables will be summarized using descriptive statistics such as number of observations (n), mean, standard deviation, median, minimum, and maximum. Categorical variables will be tabulated using frequency (n) and percent (%).

The statistical testing will be conducted at a significance level of 0.05 (two-sided) and the 95% confidence interval will be shown, unless specified otherwise. No statistical testing will be conducted for safety measures.

All data manipulations, descriptive summaries, and statistical hypothesis testing will be performed using Statistical Analysis System (SAS) Version 9.4 or later.

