6.1. Adjustments for Covariates

In general, the inferential analysis of each IOP endpoint will adjust for the baseline IOP. Detailed information on covariate adjustment is provided in [Section 8.1](#).

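### The 18 mmHg responder endpoint is tested by a valid but unadjusted chi-square; adjusting for baseline mean diurnal IOP would gain some precision at almost no cost (low priority).

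*SAP*

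**What the plan says.** SAP 8.2 covers four binary endpoints at each post-baseline visit: reductions in mean diurnal IOP of at least 20, 25 and 30%, and mean diurnal IOP at or below 18 mmHg. For all four, "the responder rates will be analyzed using the Pearson's chi-square test" on a 2×2 table, with arm differences and p-values reported. Protocol 14.7.2.2 specifies the same method: "The binary secondary endpoints will be analyzed using the Pearson's chi-square test".

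SAP 6.1 states the general rule: "In general, the inferential analysis of each IOP endpoint will adjust for the baseline IOP". It then says "Detailed information on covariate adjustment is provided in" Section 8.1, which deals only with the primary and key secondary endpoints. In SAP 8.2 the continuous secondary endpoints receive an MMRM analogous to the primary model, which has baseline IOP as a covariate. The binary endpoints do not, and SAP section 10, which lists changes from the protocol, is silent on this.

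**The concern.** The 18 mmHg endpoint differs in kind from the other three. Its threshold is fixed, so the fall needed depends on the starting point: 4 mmHg (18%) from 22 mmHg, but 16 mmHg (47%) from 34 mmHg. Baseline therefore explains part of the outcome, and a test that ignores it treats that part as noise.

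The design does not balance baseline IOP either. Randomisation is stratified only by age below or above 18, and SAP 3.1 records that no pediatric subjects were randomised. A chance baseline difference would carry into the responder difference, whereas the baseline-adjusted analysis of mean diurnal IOP at the same visit would largely remove it. At stake is precision, and agreement between two displays of the same data.

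**Working it through.** **No planned figure to reproduce.** The only power statement in the documents is that "200 subjects per treatment arm) will provide 90% power to demonstrate non-inferiority". It concerns the primary test. No responder rate, expected difference or power is given for the responder endpoints.

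**Inputs from the documents.** 200 per arm and 1:1 allocation (SAP 3.2, 3.3); two-sided 5% level (SAP 6); SD 4.0 mmHg and correlation 0.6 among repeated measures (SAP 3.3); entry at 22 to 34 mmHg (Protocol 8.1).

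**Assumed inputs.** Baseline-to-follow-up correlation ρ, responder rates, and baseline mean and SD. The 0.6 in SAP 3.3 is not said to include baseline.

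**1. Variance reduction.** Suppose baseline and follow-up are jointly normal and about half the eyes respond. Adjustment then removes a share (2/π)·arcsin(ρ²) of the variance of the risk difference. Simulation used 1,500 trials per setting, baseline mean 25.5 and SD 2.5, and follow-up SD 4.0 × √[(1 + 2×0.6)/3] = 3.4. It compared the unadjusted difference with the standardised risk difference from a logistic model.

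| ρ | Formula | Simulated variance ratio | Simulated reduction |
|---|---|---|---|
| 0.3 | 5.7% | 0.944 | 6% |
| 0.4 | 10.2% | 0.889 | 11% |
| 0.5 | 16.1% | 0.851 | 15% |
| 0.6 | 23.4% | 0.759 | 24% |

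A separate simulation over ρ = 0.3 to 0.6 gave ratios of about 0.95 to 0.82, hence the overall range of roughly 5 to 24%.

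**2. Power.** Take unadjusted power of 61%, within the simulated 60 to 62%. The standardised effect is 1.96 + 0.28 = 2.24. Dividing by the square root of each ratio above gives 2.30, 2.38, 2.43 and 2.57, so power is 63, 66, 68 and 73%. The simulation gave 65, 66, 68 and 72%.

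**3. Check under different assumptions.** Baseline was drawn from a normal distribution (mean 25, SD 3) truncated to 22 to 34 mmHg, with follow-up SD 3.0 or 4.0 and 2,000 trials per row. The chi-square was compared with the likelihood-ratio test for treatment in a logistic model containing baseline. Each cell shows the results for responder rates of about 35% vs 47%, then about 50% vs 62%.

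| ρ | Chi-square power | Adjusted power | Gain (points) |
|---|---|---|---|
| 0.23 | 65.6, 66.2 | 67.9, 67.7 | 2.3, 1.5 |
| 0.31 | 64.1, 65.2 | 68.3, 68.6 | 4.2, 3.4 |
| 0.35 | 64.9, 65.7 | 69.3, 70.2 | 4.4, 4.5 |
| 0.47 | 65.8, 65.5 | 72.4, 71.6 | 6.6, 6.1 |
| 0.58 | 65.1, 63.8 | 76.1, 77.0 | 11.0, 13.2 |
| 0.62 | 66.1, 64.1 | 78.5, 78.1 | 12.4, 14.0 |

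Hand check of the chi-square at 35.1% vs 46.6%: the pooled SE is √(2 × 0.4085 × 0.5915/200) = 0.0492 and the unpooled SE is 0.0488. Power = Φ[(0.115 − 1.96 × 0.0492)/0.0488] = 0.65, against 0.641 simulated.

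**4. Type I error.** With no true difference, rejection was 4.6% for the chi-square and 5.3% adjusted. The Monte Carlo SE over 4,000 trials is √(0.05 × 0.95/4000) = 0.34 points. Both tests are valid.

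**5. Size of a chance imbalance.** With baseline SD 2.5, the SE of the baseline difference is 2.5 × √(2/200) = 0.25 mmHg. A two-SE imbalance (0.5 mmHg, or 0.2 SD) moves a responder difference near 50% by about 0.2 × ρ × 0.40, which is 2.4 points at ρ = 0.3 and 4.8 points at ρ = 0.6. The SE of the responder difference is √(0.5/200) = 5 points.

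**6. Percent-reduction endpoints.** For the 25% endpoint, simulated variance ratios were 0.993, 1.002 and 0.993. Response means follow-up minus 0.75 × baseline is at or below zero, which removes most of the dependence on baseline when the regression slope (ρ × 3.4/2.5) is near 0.75. The 20 and 30% endpoints share this structure but were not simulated. The cancellation is not exact: at ρ = 0.3 the slope is 0.41, and the step 1 formula, using the correlation of that difference with baseline (−0.255), leaves about 4%.

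**The case against.** A reader might infer that SAP 8.2 contradicts 6.1. The documents do not support that. Section 6.1 opens with a qualifier and sends the reader to 8.1, not 8.2. The chi-square is the specific rule for binary endpoints and comes unchanged from the protocol. It is an exception that nobody has stated.

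A reader might also infer that no confidence interval is planned, since 8.2 names only differences and p-values. SAP section 6, which opens its testing rules with "The statistical testing will be conducted at a significance level of 0.05 (two-sided", makes the 95% confidence interval a default unless something else is specified. Section 8.2 specifies nothing else, so the default applies.

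A third tempting reading is that chance imbalance biases the result. It does not: such imbalance is ordinary sampling error, and the 5% level already covers it, as step 4 shows.

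The strongest remaining argument is that little depends on this test. The endpoint is among the other secondary endpoints, outside the seven-test sequence of SAP 6.4. No power is claimed for it, and planning assumes a 0 mmHg difference. Mean diurnal IOP is already analysed with baseline adjustment, baseline IOP is tabulated by arm, and SAP 8.3 examines effects by baseline below 25 or at least 25 mmHg. The size of the gain is also uncertain, and restricting entry to 22 to 34 mmHg narrows the baseline spread and so weakens the correlation. All of this stands. It sets the priority low, but it is no reason to leave a collected covariate unused.

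**Conclusion.** This is an available efficiency gain on one low-tier endpoint, and not an error. At assumed correlations of 0.3 to 0.6, adjusting the 18 mmHg endpoint reduces the variance of the risk difference by roughly 5 to 24% and adds about 3 to 12 points of power to a base of about 60%. Individual scenarios near 0.6 reach 14 points. At a correlation of 0.23 the gain is about 2 points. Type I error is unaffected.

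These figures rest on assumed responder rates, baseline distribution and correlation, and on no missing data. The direction follows from the fixed threshold and the entry range; the size cannot be settled from the documents. No primary or key secondary conclusion is touched.

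**What to change.** Before unmasking, amend SAP 8.2 so that the 18 mmHg endpoint is analysed at each visit by logistic regression on treatment and baseline mean diurnal IOP. Report the baseline-standardised risk difference with its 95% confidence interval, and keep the Pearson chi-square as supportive. Leave the 20, 25 and 30% reduction endpoints on the chi-square, and add to 6.1 that they are not adjusted for baseline. Record the change from Protocol 14.7.2.2 in SAP section 10.

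The cost is a few SAP sentences and a few lines of code. It needs no new data and no change to sample size or to the testing sequence.

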8.3. Subgroup Analyses

The homogeneity of treatment effects among prospectively defined subgroups was assessed using MMRM analyses of IOP (at each visit and timepoint) and mean diurnal IOP (at each visit) for the following subgroups:

- Age (< 65 or ≥ 65 years)
- Sex (males or females)
- Race (White or Black)
- Primary ocular diagnosis (OAG or OHT)
- Prior use of IOP-lowering medication (β -adrenergic antagonist, prostamide or prostaglandin analogue, α -adrenergic agonist, carbonic anhydrase inhibitors, or none)
- Mean diurnal IOP at baseline (< 25 or $\geq 25\text{ mmHg}$)
- Lens status (phakic or pseudophakic/aphakic)

Other subgroup analyses may be performed as deemed necessary.

9. SAFETY ANALYSES

The safety-related measures collected in this study include AEs, best-corrected visual acuity, slit-lamp biomicroscopy (severity scores for 12 parameters, ophthalmoscopy (cup-to-disc ratio, glaucomatous optic nerve severity score, and assessments of retina, macula, choroid, and vitreous), and eyelid sulcus/eyelid/eyelash/iris color. In the event that a subject took both DE-117 and Timolol during the study, the subject will be summarized with those receiving DE-117.

All the safety-related measures will be summarized descriptively by actual treatment received on the Safety population.

9.1. Adverse Events

AEs, SAEs, SARs, serious SARs, and significant AEs (AEs leading to study drug discontinuation and AEs leading to death) will be tabulated by type of AEs by treatment arm using actual treatment received for all AEs, ocular AEs, and non-ocular AEs separately.

Besides the overall AE summary, AEs, SAEs, SARs, serious SARs will be tabulated by SOC and preferred term for all AEs, ocular AEs, and non-ocular AEs separately. A subject who experienced multiple AEs within a SOC or preferred term will be counted only once for that SOC or preferred term. Non-serious AEs (including number of events) and ESIs will also be summarized by SOC and preferred term.

AEs, SAEs, SARs, serious SARs, ocular AEs, AEs leading to death, AEs leading to study drug discontinuation, non-TEAEs, and ESIs, if any, will be listed separately.

9.1.1. Ocular Inflammation

Subjects who developed AEs during the study with one of the following preferred terms will be included in the ocular inflammation summary:

- Anterior chamber cell
- Anterior chamber flare
- Eye inflammation
- Iridocyclitis
- Iritis
- Uveitis

Ocular inflammation leading to study drug discontinuation, requiring steroid treatment, or requiring NSAIDs treatment will be summarized at the subject level by frequency and percentage separately.

Ocular inflammation start time (in terms of study day) and duration of the AE will be summarized at the eye level using mean, standard deviation, median, minimum, and maximum by study eye and fellow eye separately. To allow for the computation of simple descriptive statistics, only subjects who develop ocular inflammation during the study will be used for the ocular inflammation start time summary, and only subjects who develop these AEs during the study and later resolved will be used in the duration of AE analysis.

All ocular inflammation AEs will be provided in a listing.

9.1.2. Macular Edema

Subjects who developed AEs during the study with one of the following preferred terms will be included in the macular edema summary:

- Macular edema
- Cystoid macular edema

Macular edema start time (in terms of study day) and duration of the AE will be summarized using mean, standard deviation, median, minimum, and maximum by study eye and fellow eye separately. To allow for the computation of simple descriptive statistics, only subjects who develop macular edema during the study will be used for the macular edema start time summary, and only subjects who develop these AEs during the study and later resolved will be used in the duration of AE analysis.

Change from baseline in BCVA at the onset of macular edema, when macular edema is resolved, and at the last visit will be summarized using mean, standard deviation, median, minimum, and maximum by study eye and fellow eye separately. Subjects with pseudophakic lens or phakic lens at baseline who developed macular edema during the study will be summarized by frequency and percentages separately.

The aforementioned summaries will be performed at the eye level. All macular edema AEs will be provided in a listing.

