#### **12.1.3. Events of Special Interest**

The following are considered ESIs and should be reported on the appropriate eCRF with as much information as available within 24 hours of knowledge of the event:

- Pregnancy:
  - There are no controlled data with the investigational product in human pregnancy. It is required that females of childbearing potential use effective contraception during the study and recommended for 4 weeks for female subjects of childbearing potential and 12 weeks for male subjects capable of fathering children after the completion of the study. Any pregnancy occurring during study treatment should be reported and the subject will be discontinued from the study. The subject should be followed until the end of pregnancy or until the end of the study, whichever is longer.

- Medication administration errors
  - Study medication administration errors determined to be **significant** by the Investigator will be reported and evaluated as ESIs. Examples of study medication administration errors may include, but are not limited to: incorrect dose of study medication and administration of study medication from an incorrect kit. An AE does not necessarily need to have occurred to count as a study medication administration error. A medication administration error is an unintended failure in the process of treatment with a medicinal product that leads to, or has the potential to lead to harm of the subject.
- Macular edema (including cystoid macular edema):
  - Macular edema has been reported in some patients during the DE-117 clinical trials. Any cases of macular edema (including cystoid macular edema) should be reported in the ESI form in eCRF, or in case the EDC system is down, in the manual ESI form. Any cases of macular edema (including cystoid macular edema) will need to be followed until the event is determined to be resolved, irreversible, chronic, stable, the subject withdraws consent, or no further information can be reasonably obtained as per [Section 12.1.4](#).

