#### **14.8. Safety Analyses**

All safety outcome measures will be summarized descriptively for the Safety Population. The safety outcome measures include AEs, blood pressure and pulse rate, BCVA, slit-lamp biomicroscopy findings, ophthalmoscopy, iris color, eyelash, and eyelid.

AEs will be coded using the latest version of Medical Dictionary for Regulatory Activities (**MedDRA**). Subjects with any AEs will be tabulated by primary SOC and PT specified in the MedDRA. Similarly, subjects with any ocular and non-ocular AEs will be tabulated separately. AEs, ocular and non-ocular will also be summarized by relationship to treatment and maximum severity. In addition, SAEs and discontinuations due to AEs will be summarized.

Safety parameters listed in [Section 12.2.1](#) and [Section 12.2.2](#) will be summarized using descriptive statistics by actual treatment received. Changes from baseline in these safety parameters will also be summarized by treatment.

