7.2. Demographics and Baseline Characteristics

Subject demographics and baseline characteristics will be descriptively summarized for the FAS by planned treatment. Specifically, for subject demographics, the following variables will be summarized:

- Age at randomization (continuous and categorical: < 65 years or \geq 65 years)
- Sex (categorical: Male or Female)
- Ethnicity (categorical: Hispanic/Latino or Not)
- Race (categorical: American Indian or Alaska Native, Asian, Black or African American, Native Hawaiian or Other Pacific Islander, White, or Other)

For baseline characteristics, the following variables will be summarized for study eye and fellow eye, separately:

- Primary ocular diagnosis (categorical: POAG, Pseudoexfoliative Glaucoma, Pigmentary Glaucoma, or OHT)
- Iris Color (categorical: Blue/Gray, Blue/Gray with Slightly Brown, Blue/Gray – Brown, Green, Green with Slightly Brown, Green – Brown, Yellow – Brown, or Brown)
- Prior use of IOP-lowering medications (categorical: oral/topical carbonic anhydrase inhibitors, alpha agonists, beta-blockers, prostaglandin/prostaglandin analogues, or none)
- Prostaglandin naive (Yes or No)
- Baseline lens status (categorical: phakic or pseudophakic/aphakic)
- Baseline mean diurnal IOP score and baseline IOP score at each scheduled timepoint (08:00, 10:00, and 16:00)
- BCVA (logMAR)
- Central corneal thickness (μ m)
- Glaucomatous optic nerve findings (categorical: none, mild, moderate, or severe)

- Anterior chamber angle classification (Shaffer scale; categorical: approximately 5 degrees or less, approximately 10 degrees, approximately 20 degrees, approximately 30 degrees, or approximately 40 degrees or more)
- Visual field (parameters: glaucoma Hemifield test, visual field mean deviation by device, and visual field pattern standard deviation by device)

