9.1.3. Cosmetic Change(s)

Subjects who developed AEs during the study with one of the following preferred terms will be included in the cosmetic change summary:

- Blepharal pigmentation
- Eyelash changes
- Eyelash hyperpigmentation
- Eyelash thickening
- Growth of eyelashes
- Lid sulcus deepened
- Trichiasis
- Iris hyperpigmentation

Other preferred terms might be added upon review of the AE data before database lock.

Cosmetic change(s) start time (in terms of study day) will be summarized using mean, standard deviation, median, minimum, and maximum by study eye and fellow eye separately. To allow for the computation of simple descriptive statistics, only subjects who develop cosmetic change(s) during the study will be used for the cosmetic change start time summary.

The aforementioned summaries will be performed at the eye level. All cosmetic change AEs will be provided in a listing.

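### Protocol 14.8 requires adverse events to be summarised by maximum severity; SAP 9.1 has no such table and SAP Section 10 does not declare its removal

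*SAP*

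**What the plan says.** **Severity.** Protocol 14.8, Safety Analyses: "AEs, ocular and non-ocular will also be summarized by relationship to treatment and maximum severity". Protocol 12.1.1.2 has the site record the maximum severity of each AE, and SAP 4.4.1 keeps the three-level grading by the investigator. SAP 9.1 plans AE tables by type and by system organ class and preferred term, for all, ocular and non-ocular events. It plans none by severity.

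**Focused summaries.** SAP 9.1.2: "Subjects who developed AEs during the study with one of the following preferred terms will be included in the macular edema summary". Two terms follow, macular edema and cystoid macular edema. SAP 9.1.1 uses the same construction: "Subjects who developed AEs during the study with one of the following preferred terms will be included in the ocular inflammation summary", with six terms. SAP 9.1.3, on cosmetic changes, lists eight terms and alone adds: "Other preferred terms might be added upon review of the AE data before database lock".

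**Event form.** Protocol 12.1.3: "Any cases of macular edema (including cystoid macular edema) should be reported in the ESI form in eCRF". SAP 9.1 says of these events: "Non-serious AEs (including number of events) and ESIs will also be summarized by SOC and preferred term".

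**Lens status.** SAP 7.2 summarises "Baseline lens status (categorical: phakic or pseudophakic/aphakic"), and SAP 8.3 uses the same two groups. SAP 9.1.2 splits macular edema cases into pseudophakic and phakic only.

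**The concern.** The safety objective compares DE-117 with timolol. A table of preferred terms gives how many subjects had an event in each arm but not how bad the events were. The protocol planned to show that by maximum severity. SAP Section 1 makes the SAP's analyses the basis of the clinical study report, so a table missing from the SAP is likely to be missing from the report. Because Section 10 is silent, nobody reading the SAP would know that a protocol-specified summary had gone.

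The focused summaries raise a lesser question of consistency. Macular edema is the only ocular condition that the protocol makes an event of special interest, and Protocol 12.1.3 says that it has been seen in earlier DE-117 trials. Its onset, duration, change in visual acuity and lens status are summarised only in SAP 9.1.2. If cases reach the event form by the investigator's report but reach SAP 9.1.2 by coded term, the two displays can disagree within one report.

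**Working it through.** The point rests on text and not on a calculation; the plan gives no figure to reproduce. The passages were set side by side.

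1. **Is the severity table anywhere in the SAP?** Protocol 14.8 asks for two breakdowns, by relationship and by maximum severity.
   - Relationship: covered. SAP 4.4.1.3 defines suspected adverse reactions as AEs rated related, and SAP 9.1 tabulates them.
   - Severity: not covered in SAP 9.1, nor in 9.1.1 to 9.6. The severity scores in SAP 9.3 and 9.4 are slit-lamp and optic nerve examination grades, not AE severity. The two SAP appendices, as SAP 8.1.2 describes them, hold code for the efficacy models.
   - Declared as removed? SAP Section 10 has three entries: the Full Analysis Set definition, the added key secondary endpoint, and the removal of last-observation-carried-forward. Severity is not among them.

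2. **Can the term lists grow?** SAP 9.1.1 has six terms and no clause for adding more. SAP 9.1.2 has two terms and no such clause. SAP 9.1.3 has eight terms and the clause. SAP 9.1.2 does not refer to the event form.

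3. **What would a differently coded case lose?**
   - Still shown: SAP 9.1 tabulates all treatment-emergent AEs, and ocular AEs separately, by preferred term. It tabulates and lists events of special interest, which under SAP 4.4.1.4 include macular edema and cystoid macular edema. SAP 9.4 reports shifts in the macula assessment and lists changes from normal to abnormal.
   - Lost: for macular edema, the onset, duration, visual acuity and lens summaries of SAP 9.1.2. For inflammation, which is not an event of special interest, the discontinuation, steroid, NSAID, onset and duration summaries of SAP 9.1.1.

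4. **Lens categories.** Protocol 21.3.7 records phakic, aphakic or pseudophakic. SAP 7.2 and 8.3 pool the last two. SAP 9.1.2 names only phakic and pseudophakic, so an aphakic eye with macular edema has no row in the split. It remains in the macular edema listing and in the other SAP 9.1.2 summaries.

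5. **Scale.** With the planned 200 subjects per arm, one subject is 1/200 = 0.5 percentage points. That figure could apply only to the subject-level percentages in SAP 9.1.1, and only if their denominator is the arm, which the SAP does not state. It does not apply to AE or special-interest incidence. Nor does it describe the onset, duration and visual acuity summaries of SAP 9.1.2, which are made at eye level among those with the event.

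**The case against.** A reader might infer from the closed lists that the drug's main ocular risks would be undercounted. The documents do not support that. Every treatment-emergent AE enters the preferred-term tables whatever the focused lists contain, and events of special interest have their own table and listing. Leaving out a severity table loses information about events but does not lose events, and the lens split loses a category and not a case.

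It can also be said that miscoding is hypothetical. The documents do not show which other MedDRA term a macular edema report might take, and the two listed terms match the plan's own definition of the special-interest event. Aphakic adults may be few or absent: adults with known risk factors for macular edema are excluded, although aphakia is named only in the pediatric exclusions, and SAP 3.1 says that no pediatric subject was randomised. All of this stands, and it is why these items are secondary.

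A further reading is that keratic precipitates and synechiae should be added to the inflammation list because the slit lamp grades them. That is debatable, certainly for keratic precipitates. Protocol 21.3.7 grades that item for pigmentation or precipitate, and pigmentary glaucoma is eligible, so a positive grade need not mean inflammation. SAP 9.3 already reports these parameters and lists clinically significant worsening.

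On severity, the defence is that safety is descriptive, that no test is planned, and that the safety objective does not name severity. This does not answer the point. Protocol 14.8 commits to the summary in plain terms, and the SAP neither provides it nor says that it was dropped.

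**Conclusion.** The concern holds for the severity summary: a protocol-specified comparison of the arms is absent from the SAP, and its removal is not declared. What is lost is the distribution of maximum AE severity by arm. No count, test or efficacy result changes.

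The rest is alignment. The focused summaries in SAP 9.1.1 and 9.1.2 could omit a case coded outside their lists, the macular edema summary could then differ from the special-interest table, and the lens split does not match the SAP's own categories elsewhere. The number of subjects affected cannot be derived from the documents and may be zero.

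The conclusion assumes that the SAP text is the full specification of the AE tables. Table shells are not among the documents; if they contain a severity table, SAP 9.1 needs only a sentence to say so.

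**What to change.** - **SAP 9.1:** restore AE tables by maximum severity and treatment received, for all, ocular and non-ocular events, counting each subject once at the highest grade. If the sponsor prefers to drop them, Section 10 should say so and give the reason.
- **SAP 9.1.2:** select cases by the listed preferred terms or by any AE reported as macular edema on the special-interest event form, so that this summary agrees with the special-interest table.
- **SAP 9.1.1 and 9.1.2:** add the pre-lock term review that SAP 9.1.3 already has, and state in all three that it is done before unmasking. The SAP 9.1.3 wording fixes database lock as the limit but does not mention masking.
- **SAP 9.1.2:** use phakic versus pseudophakic/aphakic, as in SAP 7.2 and 8.3.

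The cost is one standard table set from data already graded, a few lines of SAP text, and two more lists in a review already foreseen for cosmetic terms. No new data are needed.
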